#### Equation 2. PK Model Selection Criterion

$$AIC = N * \ln(SSQ) + 2p$$

Here, N is the number of samples,  $\ln(SSQ)$  is the natural logarithm of the sum of the squared residues, and p is the number of model parameters. The model yielding the lowest AIC will be chosen.

Secondarily, standard parameters such as mass, body surface area, and body mass index will be assessed to determine if their inclusion will improve a joint parameter estimation using all subjects tested for a given agent dose. In the case that dosing for an agent was

terminated due to high AE, then such analyses will only be performed if sufficient subjects are available.

Standard PK parameters will then be calculated as appropriate to the modeling form (one or two compartmental model).

Differences between the absorption rate parameters and standard PK parameters will be assessed.

It is recognized that in some subjects, surgery may have already occurred before plasma  $C_{max}$  is reached.

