**Table 1: PK - Plasma Fulvestrant Level Schedule**

PK - Plasma Fulvestrant Level Blood Draw Schedule (Intramuscular and Intraductal)
Pre-fulvestrant – single blood sample for baseline
Post fulvestrant administration:

• 4.5 hours, Subjects are discharged following the 4.5 hour blood collection

• Day 7

• Pre-surgery

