### 13.3 Plasma Concentration Levels

The statistical analysis used for the pharmacokinetic (PK) population study may employ one or more of several advanced analysis packages including WinNonlin, Kinetica, Matlab, or R. For each subject, plasma level time curves will be assessed individually for the absorption rate and body compartment parameters. Both a one compartment and a two-compartment model will be considered. The literature values will be used for the initial conditions of the body compartment parameters, and a weighted nonlinear routine will be used for the parameter estimation. The optimal model will be chosen based on the Akaike Information Criterion (AIC).

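### Subject-by-subject AIC cannot choose between one- and two-compartment PK models from three post-dose samples, and Equation 2 does not say whether its SSQ is weighted

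*Combined protocol and SAP*

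**What the plan says.** Section 13.3 sets the level of the fit: "For each subject, plasma level time curves will be assessed individually for the absorption rate and body compartment parameters". On the candidates it says "Both a one compartment and a two-compartment model will be considered", and on estimation that "a weighted nonlinear routine will be used for the parameter estimation". Literature values supply starting values only. The model with the lowest AIC is kept, and the standard PK parameters are then derived according to its form.

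Equation 2 gives AIC = N ln(SSQ) + 2p. Its legend says that "N is the number of samples" and that the log term "is the natural logarithm of the sum of the squared residues". It does not say whether these residuals are weighted, and no weights are given anywhere.

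Table 1 lists one pre-dose draw ("single blood sample for baseline") and three post-dose draws. The first is "4.5 hours, Subjects are discharged following the 4.5 hour blood collection"; the others are on Day 7 and before surgery.

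A joint fit over all subjects comes second in Section 13.3, to test body-size covariates. Section 13.0 names a population PK analysis. Neither has its own rule for choosing the structural model, and no rule covers the case where parameters equal or outnumber samples.

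**The concern.** AIC trades goodness of fit against the number of parameters, so it needs residual variation to work on. When a model has as many parameters as there are data points, it can pass through all of them. SSQ is then zero and its logarithm does not exist. A model with more parameters than points also has no unique solution.

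The selected model decides which PK parameters are calculated and compared between intramuscular and intraductal dosing, which is secondary objective b in Section 6.2. If the selection is numerical noise, subjects may be given different structural models for no pharmacological reason, and their parameters are then not comparable.

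A second, smaller point is that the fit is weighted while the selection formula shows no weights. The reader cannot tell whether the quantity minimised is also the quantity ranked.

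**Working it through.** The plan gives no figure to reproduce, so I counted samples against parameters and evaluated Equation 2 directly.

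**Inputs from the plan.** Three post-dose samples per subject (Table 1); individual fits, two candidate models and weighted estimation (Section 13.3); 30 subjects (Section 13.2).

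**Assumed, because the plan gives none.** First-order absorption, with p = 3 (absorption rate, elimination rate, scaled volume) for one compartment and p = 5 for two; sampling at 4.5 hours, Day 7 and Day 14; 20% proportional error; all concentrations and rate constants.

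**1. Degrees of freedom per subject (N - p).** One compartment: 3 - 3 = 0. Two compartments: 3 - 5 = -2. Counting the pre-dose sample raises N to 4 but does not help, because both models predict zero at time 0 whatever their parameters. A small-sample AIC correction is unusable: its denominator N - p - 1 is -1 and -3.

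**2. Equation 2 on exact fits.** The three-parameter model was fitted to three illustrative profiles, once without weights and once with 1/C² weights. Equation 2 was then evaluated with the plain SSQ:

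| Profile | Unweighted fit: SSQ, AIC | Weighted fit: SSQ, AIC |
|---|---|---|
| 2, 8, 6 | 4.9e-30, -196.4 | 1.0e-29, -194.2 |
| 1, 5, 4.5 | 0, minus infinity | 4.0e-30, -197.1 |
| 4, 10, 6 | 3.9e-30, -197.1 | 3.6e-29, -190.5 |

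Every fit is exact, so these AIC values are rounding error. In the last row the same model on the same data differs by 197.1 - 190.5 = 6.6. The whole penalty difference between the candidates is 2 × 5 - 2 × 3 = 4.

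**3. How often this happens.** 100 subjects per scenario were simulated from a one-compartment model. A fit counted as exact if its weighted SSQ was below 1e-10.

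| Scenario | One-compartment exact | Two-compartment exact | Both exact | Only two-compartment exact | Neither exact |
|---|---|---|---|---|---|
| Slow absorption (0.25 per day) | 36% | 62% | 36% | 62 - 36 = 26% | 100 - 62 = 38% |
| Faster absorption (1.0 per day) | 89% | 98% | 89% | 98 - 89 = 9% | 100 - 98 = 2% |

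Where both are exact, AIC cannot rank them. Where only the two-compartment fit is exact, ln(SSQ) heads to minus infinity and overrides the penalty, although the data came from one compartment. Where neither is exact, the requirement that rate constants be positive prevents interpolation. N - p is still 0 or -2.

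**4. Pooled.** 30 × 3 = 90 post-dose samples. With the same p, N - p - 1 is 90 - 3 - 1 = 86 and 90 - 5 - 1 = 84, so the correction is defined.

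**5. Whether the weighting could matter.** Take concentrations 1, 10, 5, equal p, and invented residuals A = (0.9, 0.2, 0.2) and B = (0.05, 1.5, 0.6).
- Unweighted: SSQ is 0.89 and 2.6125, so 3 ln(SSQ) is -0.35 and 2.88, and A is chosen.
- With 1/C² weights: SSQ is 0.812 and 0.0394, giving -0.62 and -9.70, and B is chosen.

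This shows only that the definition can matter, not that it would change the comparison in this trial.

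**The case against.** The strongest reply is that little depends on this. PK is a secondary objective, Section 6.2 calls the profile abbreviated, and Section 13.2 compares the routes only qualitatively. No sample size or decision rule uses the compartment choice. Section 13.0 foresees a population analysis and a detailed SAP before database lock, where the details could be settled. All of this stands and limits the severity. It does not make the stated rule workable, because the joint fit and the population analysis carry no structural-model rule, and Section 13.3 assigns selection to the individual fits.

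A reader might also infer three stronger claims that the documents do not support.

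- *Equation 2 uses an unweighted SSQ.* The legend does not say so. It follows directly on a sentence about weighted estimation, so the weighted quantity may be intended. This is a missing definition, not a proven formula error.
- *The highest concentrations drive the choice.* That requires both an unweighted SSQ and error that grows with concentration. The plan gives no error model and no expected concentrations.
- *A saturated model always fits exactly.* It often does, but under slow absorption the one-compartment fit was exact in only 36% of simulated subjects. Slow uptake is what Section 5.1 expects for intraductal dosing.

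The two issues also have different causes. Saturation comes from sparse sampling combined with individual fitting. Weighting SSQ does not cure it, since a zero residual stays zero under any weight.

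**Conclusion.** The point holds in this form: with three informative samples per subject, the selection rule in Section 13.3 cannot validly rank a one- against a two-compartment model. Under the assumed counts of 3 and 5 parameters, residual degrees of freedom are 0 and -2 for every subject. The share of subjects in whom both fits are exact, 36% and 89% in the two scenarios, depends on assumed rate constants, error and starting values. It shows that the problem is common, not how common it will be here. The unstated weighting of SSQ is a separate gap in definition. The consequence is confined to the PK comparison of routes. The matter is minor and worth correcting before the analysis.

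**What to change.** Reword Section 13.3 so that the joint or population fit comes first. Select the structural model once on that fit, across subjects (about 90 post-dose samples), by the lowest -2 log-likelihood + 2p, with a small-sample correction if wanted. Drop AIC selection subject by subject. If Equation 2 is kept in any form, state that SSQ uses the same weights as the fit, and give those weights.

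The cost is a short rewrite of Section 13.3, or the corresponding text in the promised SAP; no new data are needed. The downside is that all subjects share one structural model. Pooling also makes the criterion defined without adding information about a second compartment. With samples clustered around three times, the simpler model may well be chosen, and the report should say why.

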### **13.4 Tissue Concentration**

The fulvestrant concentration in the breast tissue will be determined from the specimen obtained during the pathology examination of the tissue excised during surgery.

## **14.0 DIRECT ACCESS TO SOURCE DATA/DOCUMENTS**

The investigator is responsible for maintaining any original source data documentation related to the study, the subject identification list and all original signed informed consent form(s) as outlined in Section 17.6, Record Retention. Study-specific CRFs must be completed for each subject enrolled in the study as outlined in Section 17.1, Recording of Data.

### **14.1 Access to Source Documents**

Atossa Genetics is responsible for assuring that the data collected is complete and accurate. The most effective way to assure the accuracy of the data is to review individual subject records and other supporting documents and compare those records with the reports prepared by the investigator for submission to the sponsor. Therefore, during a periodic visit, the monitor will compare a representative number of subject records and other supporting documents with the investigator's reports to determine that:

- The information recorded in the investigator's report is complete, accurate and legible.
- There are no omissions in the reports of specific data elements such as the administration to any subject of concomitant study drug or the development of an intercurrent illness.
- Missing visits or examination are noted in the reports.
- Subjects failing to complete the study and the reason for each failure are noted in the reports.
- There is no evidence of fraud or data falsification.

### **14.2 Monitoring**

In accordance with regulatory guidelines as outlined in 21 CFR 312, the sponsor is required to monitor the progress of a clinical investigation. Proper monitoring is necessary to assure adequate protection of the rights of human subjects, the safety of all subjects involved in clinical investigations, and the quality and integrity of the data.

Following the conduct of the study initiation visit, Atossa or its representatives (e.g., CRA or representative contracted to support this clinical trial) may attend and observe some of the

study related intraductal procedures and data collection at the institution to ensure proper conduct of the study. The investigator will permit all CRA to monitor the study as frequently as the CRA deems necessary in order to ensure that the clinical facilities remain acceptable and that data recording and protocol adherence remain satisfactory. The CRFs and related source documents will be reviewed per the monitoring plan. This includes tests performed as a requirement of participation in the study (e.g., history, intraductal administration of any agent, imaging, pathology, and reports) and may include other medical records required to confirm the information contained in the CRFs.

During the review of these documents the anonymity of the study subject will be maintained with strict adherence to professional standards of conduct/and confidentiality.

Prior to each monitoring visit, the investigator should record all data generated since the last visit in each subject's CRFs. The investigator and staff will be expected to cooperate with the CRA, to be available during at least a portion of the monitoring visit to answer questions, and to make corrections and provide missing information as is deemed necessary.

The CRA will record the date of each visit in the Monitor Sign-In Log and will document all findings and a summary of the study status and progress in a monitoring report. Any proposed actions will be discussed with the investigator and will be confirmed in writing.

#### **14.3 Written Monitoring Procedures**

Written procedures for monitoring clinical investigations will be followed to assure the quality of the study and to assure that each person involved in the monitoring process carries out his or her duties.

#### **14.4 Monitoring Visits**

The schedule of monitoring visits will be detailed in the monitoring plan.

#### **14.5 Audits and Inspections**

Authorized representatives of Atossa or a regulatory agency, may visit the site to perform audits or inspections, including source data verification. The purpose of an Atossa audit or inspection is to systematically and independently examine all study-related activities and documents to determine whether these activities were conducted, and data were recorded, analyzed, and accurately reported according to the protocol, Good Clinical Practice guidelines of the International Conference on Harmonization, and any applicable regulatory requirements. The investigator should promptly contact the Atossa representative if contacted by a regulatory agency about an inspection.

### **15.0 QUALITY CONTROL AND QUALITY ASSURANCE**

#### **15.1 Investigator Selection**

Prior to the initiation of the clinical trial, the investigator and any co-investigators must provide Atossa with copies of their current licensure and *curriculum vitae*, including a list of publications and any other relevant documentation requested by the sponsor, the Institutional Review Board (IRB) and/or regulatory agencies.

The investigator (s) shall meet all the qualifications specified by the applicable regulatory requirement (s) of Title 21 Code of Federal Regulations (CFR) Part 312.53, shall provide evidence of such qualifications, and shall be qualified by the sponsor based upon:

- Education
- Training and experience to assume responsibility for the proper conduct of the trial
- Professional standing and experience (including licensure)
- Professional referrals
- Authors of pertinent publications
- Investigator workload
- Adequate access to study population

In addition to investigator qualifications, institutions must meet the following criteria:

- Experience in conducting clinical trials
- Adequate access to study population(s)
- Qualifications and availability of study site personnel
- Adequate equipment and facilities to conduct clinical trial procedures

### **15.2 Changes to the Protocol and Study Related Procedures**

No change in the study protocol or any study related procedure may be implemented without the mutual, written agreement of the investigator and the medical monitor of Atossa. All changes must be documented by signed protocol amendments that are agreed to and signed by Atossa; copies provided to the IRB/IEC; and the IC revised if necessary. Trial participants may need to be re-consented depending on the nature of any protocol amendments.

It is the responsibility of Atossa to distribute any proposed amendment to the investigator at each clinical site. The investigator is responsible for the distribution of any amendments to all relevant staff concerned with the conduct of the study at the study site, as well as to the IRB.

### **15.3 Study Termination by the Sponsor**

The Sponsor reserves the right to prematurely terminate the study if, in the opinion of the sponsor, there is sufficient reasonable cause. Sponsor will make every effort to provide 30-days written notice of study termination, except when the reason for termination concerns subject safety, in which case the clinical trial may be discontinued immediately. Written notification documenting the reason for such a termination will be provided to the investigators. Circumstances that may warrant termination include, but are not limited to:

- Determination of unexpected, significant or unacceptable risk to the subjects
- Overall failure to enroll study subjects at an acceptable rate
- Plans to modify, suspend or discontinue the development of the study product/procedure

### **15.4 Site Termination by the Sponsor**

Sponsor has the right to terminate an individual study site and remove all study materials from a site at any time. Reasons for termination of a study site may include, but are not limited to the following:

- It is apparent that subject enrollment is unsatisfactory with respect to quality and/or quantity of potential study subjects
- Data recording is inaccurate and/or incomplete on a consistent basis
- Insufficient adherence to protocol requirements

- Inadequate informed consent of study subjects
- Integrity of data is questionable or unable to be verified
- Preliminary data/outcomes at this study center indicate that the study product poses an unacceptable risk/health hazard to study participants.
- Consistent failure to adhere to GCPs.

### **15.5 Good Clinical Practices**

This study will be conducted in accordance with International Conference on Harmonization, (ICH) Guidelines for GCPs and the appropriate regulatory requirement(s) of Title 21 CFR Parts 11, 50, 54, 56, 312 and 314, with the overall purpose of ensuring the safety and well-being of the participating trial subjects. The investigator will be thoroughly familiar with the appropriate use of the study product(s) and procedure(s) as described in this protocol. Essential clinical documents will be maintained to demonstrate the validity of the study and the integrity of the data collected. Master files will be established at the beginning of the study, maintained for the duration of the trial and retained according to the requirements outlined in this protocol and all appropriate regulations.

### **15.6 Protocol Compliance**

The investigator will conduct the trial in compliance with the protocol and after approval/favorable opinion by the IRB and the appropriate regulatory authority(ies). Modifications to the protocol should not be made without agreement of both the investigator(s) and the sponsor. Changes to the protocol will require written IRB approval/favorable opinion prior to implementation, except when the modification is needed to eliminate an immediate hazard(s) to subjects or if the change(s) involves only logistical or administrative aspects of the trial. The IRB may provide, if applicable regulatory authority(ies) permit expedited review and approval/favorable opinion for minor change(s) in ongoing trials that have the approval of the IRB.

When immediate deviation from the protocol is required, the investigator will contact the medical monitor, if the circumstances permit, to discuss the planned course of action. Any departures from the protocol must be fully documented in the CRFs and source documentation.

## **16.0 ETHICS**

The study will be performed in accordance with ethical principles that have their origin in the Declaration of Helsinki 1989 and in compliance with 45 CFR part 46 and are consistent with ICH Good Clinical Practice, and applicable regulatory requirements.

In order to safeguard the rights, safety and wellbeing of the subjects in this study, the study protocol, subject information, subject informed consent form (ICF), and copies of any proposed advertisements to be used (if applicable), must be reviewed and receive the approval of an IRB/IEC. The opinion and notification of approval by the IRB should be given in writing and should refer to this study by title, version date and study number. In addition, a list of those present at the IRB meeting, with their positions and institutional affiliations clearly stated, should be attached whenever possible.

It is the responsibility of each investigator to forward a copy of the notification of IRB approval for both the protocol and the subject ICF to Atossa prior to the start of study

enrollment at each study center when multiple centers participate.

The investigator will also ensure that all changes in the approved research activities, and all unanticipated problems involving risks to the subjects in the study are promptly reported to the IRB; and that no changes will be made to the protocol without IRB approval, except when necessary to eliminate apparent immediate hazards to the subject. For minor changes to previously approved research, it may be possible for the investigator to secure an expedited review by the IRB as provided for under 21 CFR Part 56.110.

As part of the IRB requirement for continuing review of approved research, the investigator will be responsible for submitting periodic progress reports to the IRB at intervals appropriate to the degree of subject risk involved, but no less than annually. All correspondence to and from the IRB should be filed by the investigator in the study specific regulatory files. Copies of all such correspondence as well as notification of continued IRB approval of this trial, or withdrawal of such approval, must immediately be forwarded to Atossa by the study investigator.

All safety updates, annual progress reports and any revisions to the aforementioned documents will be provided to the IRB by the investigator. No change in study conduct will be made without the prior written approval of the IRB.

The investigator acknowledges that his/her institutional approval to conduct this clinical trial is limited to the site of investigation specified in the submission to the reviewing IRB.

### **16.1 Subject Information and Informed Consent**

In accordance with guidelines as outlined in CFR 21 Part 50, the investigator will ensure that the subject or the subject's legal representative (as appropriate) are provided full and adequate verbal and written information about the nature, purpose, possible risks and benefits of this study. They must also be notified that they are free to discontinue their participation in this study at any time. The subject will not be entered into the trial nor will any non-routine procedures be performed prior to obtaining written informed consent from the subject.

The subject and/or the subject's legal representative should retain a copy of the signed ICF. Should modifications be made to the current ICF, the revised IRB approved version of the ICF must be signed by the subject and or the subject's legal representative prior to the institution of any proposed change in study conduct. The ICF outlines the procedures and requirements associated with participation in this clinical trial.

